4.2.3.2. Bayesian inference for time-to-event outcomes with covariate adjustment

We assume here that the data satisfies the Cox proportional hazards assumption, that is –

$$\log h(t; x, T, \beta, \gamma) = \log h_0(t) + x^T \beta + \gamma T,$$

where $h_0(t)$ is the baseline hazard function and $h(t; x, T, \beta, \gamma)$ is the hazard function of an individual with covariate vector x who was assigned to treatment T , evaluated at time t .

We model the baseline hazard as a piecewise constant function

Statistical Analysis Plan

Sponsor:	McMaster University		
Protocol:	TOGETHER trial		
Document Version No.:	1.1	Document Date:	05-May-2021

$$h_0(t; \boldsymbol{\lambda}) = \sum_{j=1}^J \lambda_j \mathbb{I}(t \in (a_{j-1}, a_j]) \quad (1)$$

as in Ibrahim et al.⁴ for $\lambda_1, \dots, \lambda_J \geq 0$ and some partition $a_0 = 0 < a_1 < \dots < a_J = t_{max}$ of the real line with t_{max} the end of the follow-up period. This induces the baseline survival function

$$S_0(t; \boldsymbol{\lambda}) = - \sum_{j=1}^J \lambda_j (t - a_{j-1}) \mathbb{I}(t \in (a_{j-1}, a_j]), \quad (2)$$

and, denoting $\mathbf{t} = [t_1, \dots, t_n]^T$ the vector of event times, the log-likelihood function is given by

$$\ell(\mathbf{t}; \boldsymbol{\beta}, \gamma, \boldsymbol{\lambda}) = \sum_{i=1}^n [(1 - \delta_i) \log h_0(t_i; \boldsymbol{\lambda}) + x_i^T \boldsymbol{\beta} + \gamma T_i + \log S_0(t_i; \boldsymbol{\lambda}) + \exp(x_i^T \boldsymbol{\beta} + \gamma T_i)], \quad (3)$$

where δ_i is an indicator assuming the value of 1 if the i^{th} observation was right-censored and 0 otherwise. We may then assign an improper, independent prior $p(\boldsymbol{\beta}, \gamma, \boldsymbol{\lambda}) \propto \prod_{j=1}^J \lambda_j^{-1}$, and proceed to generate an MCMC sample from the posterior distribution, using the log-posterior

$$\log p(\boldsymbol{\beta}, \gamma, \boldsymbol{\lambda} | \mathbf{t}) = \text{const} + \ell(\mathbf{t}; \boldsymbol{\beta}, \gamma, \boldsymbol{\lambda}) - \sum_{j=1}^J \log \lambda_j$$

within a Metropolis-Hastings scheme. Inference on treatment efficacy, as always, will be based on the $100(1 - \alpha)\%$ credible interval for γ .

The treatment effects on time-to-event outcomes will be estimated using R.

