4.2.3.2.1. Checking for proportional hazards assumption for time-to-event analyses

The proportional hazards assumption will first be checked visually inspecting the Kaplan-Meier plots of the survival function versus the survival time. Plots of $\log(-\log(\text{survival}))$ versus $\log(\text{survival})$ will also be generated to check the proportional hazards assumption.

Statistical Analysis Plan

Sponsor:	McMaster University		
Protocol:	TOGETHER trial		
Document Version No.:	1.1	Document Date:	05-May-2021

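### The likelihood printed for the secondary time-to-event endpoints is not a valid piecewise-exponential likelihood, and one of the two proportional-hazards plots carries no information

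*SAP*

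**What the plan says.** SAP section 4.2.3.2 begins "We assume here that the data satisfies the Cox proportional hazards assumption" and continues "We model the baseline hazard as a piecewise constant function", with level λ_j on the interval from a_{j-1} to a_j. The partition is left open.

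It then states "This induces the baseline survival function" and prints equation (2): "S_0(t; \boldsymbol{\lambda}) = - \sum_{j=1}^J \lambda_j (t - a_{j-1}) \mathbb{I}(t \in (a_{j-1}, a_j".

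In the log-likelihood, equation (3), the event part reads "1 - \delta_i) \log h_0(t_i; \boldsymbol{\lambda}) + x_i^T \boldsymbol{\beta} + \gamma T_i", where the factor (1 - δ) closes before log h0. The survival part reads "\log S_0(t_i; \boldsymbol{\lambda}) + \exp(x_i^T \boldsymbol{\beta} + \gamma T_i". The text defines δ_i as follows: it "is an indicator assuming the value of 1 if the" observation is right-censored, and it is 0 otherwise.

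The prior is flat in β and γ and proportional to the product of 1/λ_j. Metropolis-Hastings sampling is to use the resulting log-posterior, and efficacy inference rests on the credible interval for γ. Estimation is to be in R, with no package named for this model.

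Section 4.2.3.2.1 lists two visual checks. The first is Kaplan-Meier plots against survival time. The second is log(-log(survival)) against log(survival); these plots "will also be generated to check the proportional hazards assumption".

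**The concern.** The hazard model in the first lines of section 4.2.3.2 determines the likelihood completely, and equations (2) and (3) differ from it in several places. The section says that sampling will use this log-posterior, so the equations are the stated estimator and not mere background. The endpoints concerned are time to clinical improvement, time to clinical failure and time to COVID-19 hospitalization (section 2.5.1 and Table 3). An analyst cannot carry out the plan as written and would have to substitute an unstated model, possibly after seeing data. The second proportional-hazards plot is also uninformative as described.

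**Working it through.** The SAP gives no numerical result for this model, so there is no figure to reproduce. The check derives the likelihood from the SAP's own hazard model and compares it with the print.

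**1. What the hazard model implies.** For t in interval j, the cumulative baseline hazard is H0(t) = sum over k<j of λ_k(a_k - a_{k-1}) + λ_j(t - a_{j-1}), and S0(t) = exp(-H0(t)). A patient's survival is S0(t) raised to the power exp(x'β + γT). With δ = 1 for censored, the log-likelihood is the sum over patients of (1 - δ_i)[log h0(t_i) + x_i'β + γT_i] - H0(t_i) exp(x_i'β + γT_i).

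**2. Equation (2).** As printed, S0(t) = -λ_j(t - a_{j-1}), which is at most 0, so log S0 in equation (3) is undefined. Suppose (2) was meant as log S0. The hazard of earlier intervals is still missing. For illustration, take 15% events by day 28 (the SAP's control rate) with a constant hazard, and assume cut points at 0, 7, 14 and 28 days. Then λ = -log(0.85)/28 = 0.005804 per day.
- Day 7: exp(-7λ) = 0.960.
- Day 7.01: exp(-0.01λ) = 0.9999, so survival jumps back up.
- Day 28: exp(-14λ) = 0.922, where the model gives 0.850.

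The sizes depend on the assumed cut points. The upward jump occurs at any interior cut point.

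**3. Equation (3) as printed.** With (2) read as log S0, the derivative in γ is the sum of T_i[1 + exp(x_i'β + γT_i)]. This is positive for every γ and does not involve the event data. One data set was simulated with 681 patients per arm, 28-day rates of 15% and 9.375% (a 37.5% reduction), no covariates, and the cut points above:

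| γ | -5 | -1 | 0 | 1 | 5 |
|---|---|---|---|---|---|
| Printed (3) | -3,717 | -747 | 365 | 2,216 | 104,158 |
| (3) with only the bracket restored | -652 | -134 | 365 | 1,603 | 101,093 |
| Derived likelihood | -1,339 | -1,105 | -1,103 | -1,215 | -16,173 |

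The first two rows rise throughout. The derived likelihood, maximized jointly over γ and λ, peaks at γ = -0.466 (hazard ratio 0.63; simulated truth -0.501, or 0.61).

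**4. If the plus sign is a misread product.** The bracket fault remains: censored patients still contribute x'β + γT. Let n_T be the number treated and D the total events. Raise γ by c and multiply every λ_j by exp(-c). The log-likelihood changes by c(n_T - D) + (1 - exp(-c)) × (control-arm sum of H0 exp(x'β)). The second term is never negative, so the likelihood is unbounded whenever D < n_T.
- Expected events at the planning rates for one arm and control: 681 × (0.15 + 0.09375) = 166, against n_T = 681.
- In the simulated data D = 174 and the control-arm sum is 102.4. Starting from -1,103, c = 5 gives -1,103 + 5 × 507 + 0.993 × 102.4 = 1,534. Likewise c = 10 gives 4,070 and c = 20 gives 9,140.

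When D > n_T the answer is finite but wrong. Take equal arms of size n with no true effect, the same event proportion p and the same exposure E_j in each interval, and no covariates. The score for λ_j gives λ_j E_j = D_j/(1 + exp(γ)). The score for γ gives n = exp(γ) × sum of λ_j E_j. With D = 2pn, the two give exp(γ) = n/(D - n) = 1/(2p - 1), where the correct value is 1. Over assumed values of p:

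| p | 0.60 | 0.80 | 0.90 | 0.95 |
|---|---|---|---|---|
| Spurious hazard ratio | 5.00 | 1.67 | 1.25 | 1.11 |

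**5. Prior.** Even under the correct likelihood, an interval with no event and total exposure e > 0 contributes the integral of exp(-eλ)/λ, which diverges at 0. No cut points are fixed that would rule this out.

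**6. Second diagnostic plot.** With horizontal axis x = log(survival), the vertical axis is log(-x) identically. A reference curve, a proportional curve and a non-proportional curve all lay on that line with deviation 0. Against log(time), the proportional pair (hazard ratio 0.5) showed a constant gap of -0.69. The gap for the non-proportional pair ran from -3.04 to +0.29.

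**The case against.** The strongest reply is that these are transcription slips. The plus sign is one symbol, exposed to misreading from PDF. With a product in its place and λ held fixed, γ has a finite maximum. That holds only for fixed λ; step 4 shows that the joint likelihood, which is what would be sampled, stays unbounded for uncommon events. One misread symbol also cannot explain the missing exponential, the missing earlier intervals and the misplaced bracket together. What stands is that divergence for every data set belongs to the printed plus sign only.

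A reader might infer that the trial would report a plausible but wrong hazard ratio. The document does not show that. Code written literally would take the log of a negative number or diverge, and either failure would be noticed. The section cites a standard text for the hazard model, and working R code may well be correct. A finite, biased answer arises only under the product reading with common events.

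A reader might also infer that the diagnostics would always appear to support proportional hazards. They would not. The Kaplan-Meier plots against time can show crossing or late-separating curves, and exactly coincident log-log curves would look odd beside them. The word time has probably been dropped from the axis label.

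The prior problem is conditional: it needs an interval with no event, and the SAP shows none.

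**Conclusion.** The point holds for the text as written. Equations (2) and (3) do not define a valid likelihood, and no single-symbol repair makes them valid. As printed, with (2) read as log S0 and the flat prior, γ has no credible interval. Under the product reading, the likelihood is unbounded when events are fewer than treated patients, and γ is biased otherwise. The log-log plot as described is uninformative.

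The reach is limited to secondary time-to-event endpoints. A reader might infer that the trial's main conclusion is at risk. It is not: the primary composite is binary, and the interim and final decisions use the beta-binomial model of section 4.3 and the Appendix. This is a needed correction to secondary analyses, not an obstacle to the primary one.

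The unboundedness results are algebraic. The survival values in step 2 rest on assumed cut points and a constant hazard. The count of 166 applies the planning rates to a time-to-event endpoint, and the spurious hazard ratios rest on the assumed event proportions shown.

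**What to change.** In section 4.2.3.2, replace equation (2) with the H0 and S0 of step 1, and equation (3) with the log-likelihood there, so that (1 - δ_i) covers the whole event term and the exponential multiplies -H0(t_i). Replace the 1/λ_j prior with a proper, weakly informative Gamma prior for each λ_j and state its parameters. Fix the cut points in advance, or state that they will be chosen on pooled blinded data. In section 4.2.3.2.1, plot log(-log(survival)) against log(time) by arm.

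The cost is SAP wording and a check that the R code matches. No patients, data collection or primary-analysis rules change.

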4.2.3.2.1. Checking for proportional hazards assumption for time-to-event analyses

The proportional hazards assumption will first be checked visually inspecting the Kaplan-Meier plots of the survival function versus the survival time. Plots of $\log(-\log(\text{survival}))$ versus $\log(\text{survival})$ will also be generated to check the proportional hazards assumption.

Statistical Analysis Plan

Sponsor:	McMaster University		
Protocol:	TOGETHER trial		
Document Version No.:	1.1	Document Date:	05-May-2021

4.2.4. Multiple Comparisons/Multiplicity

All subgroup analyses are considered exploratory for this stage of the TOGETHER trial and thus do not require adjustment for multiplicity. Treatment comparisons in focus are solely experimental versus placebo comparisons and for each treatment a matching placebo exists. Thus, all placebo comparisons can be considered approximately independent and therefore not requiring multiplicity adjustments. Lastly, multiplicity due to repeated testing is handled with Bayesian stopping rules (see section 4.3).

4.2.5. Subpopulations

The following subpopulations will be considered for subgroup analyses:

- Age:
 - ≥ 50 years or < 50 years
- Sex: Male or female
- Time from onset of symptoms:
 - ≥ 120 hours or < 120 hours
- Comorbidity in screening
 - Diabetes mellitus (yes or no);
 - Cardiovascular disease (yes or no);
 - Lung disease (yes or no);
 - Immunosuppressed patients / use of corticosteroid therapy (Yes or No);
 - Other special categories (solid organ transplantation, end-stage kidney disease);

Statistical Analysis Plan

Sponsor:	McMaster University		
Protocol:	TOGETHER trial		
Document Version No.:	1.1	Document Date:	05-May-2021

4.2.6. Withdrawals, Dropouts, Loss to Follow-up

Subjects who withdrew from the study will not to be replaced.

4.2.7. Missing, Unused, and Spurious Data

All data recorded on the CRF will be included in data listings that will accompany the clinical study report. Due to the design of the study and retention activities, we expect to be able to measure outcomes on all or the vast majority of participants. Multiple imputation will be employed where statistical models require adjustment for baseline covariates with up to 20% missing values. No multiple imputation of outcomes will be performed.

4.2.8. Visit Windows

Table 1 Evaluation Intervals for Efficacy Analysis

Evaluation	Protocol-Specified Interval	Interval for Analysis
Baseline	Day 0	Day 0 to Day 1
Treatment period	Day 1 to 3 or Day 1 to Day 10	Day 0 to Day 10 (Day 3 and Day 7 \pm 1 day)
End-of-Therapy	Day 3 or Day 10	Day 10 (\pm 2 days)
Post-Treatment	Day 11 to Day 60	Day 14 (\pm 2 days); Day 28 (\pm 3 days); Day 60 (\pm 5 days)

Actual dates and times will be used for pharmacokinetic analyses rather than nominal days and times.

Statistical Analysis Plan

Sponsor:	McMaster University		
Protocol:	TOGETHER trial		
Document Version No.:	1.1	Document Date:	05-May-2021

4.3. Interim Analyses

Three interim efficacy analyses are planned. Assuming a uniform prior assigned to the different event rates, a total sample size of 681 patients per arm, a CER of 15%, and a RRR equals to 37.5%, we will do an interim analysis after observing 25%, 50% and 75% of the maximum number of patient outcomes, as well as at the trial completion. The posterior efficacy threshold will be 97.6% and the futility threshold will be 20%, 40% and 60%. Intervention arms(s) showing a posterior probability of efficacy crossing either boundary, will be stopped for either reason. These superiority and futility thresholds were determined based on 200,000 simulation runs in which different values of the RRR were considered (0%, 20%, and 37.5%). A description of this interim analysis in an event-based Bayesian adaptive trial and accompanying illustrating example can be found in the appendix of this document.

4.3.1. Sample Size Re-Assessment for Brazil

Given that intervention arm(s) are neither superior or futile at the time of the first interim analysis for binary outcome analysis, sample size re-assessment will be performed based on COVID-19 related hospitalization or emergency room visit (for patients under observation for 6 hours or more). For binary outcomes, the sample size and the observed number of events in the control and treatment arms at the time of interim analysis will be used to calculate the future sample size required to achieve 90% BPP. The technical details can be found in Harari and colleagues' paper published in the Pharmaceutical Statistics.⁵

4.3.2. Borrowing Strengths from External Studies

Should individual patient data (IPD) from other relevant studies become available, we may use Empirical Bayes IPD meta-analysis⁶ to borrow information from the treatment effects emerging from these studies. This is effectively a random effect Bayesian model that results in simultaneous shrinkage of the treatment effect estimates reported in the various studies toward

Statistical Analysis Plan

Sponsor:	McMaster University		
Protocol:	TOGETHER trial		
Document Version No.:	1.1	Document Date:	05-May-2021

the meta-analysis estimate, while still providing standalone estimates. Schoenfeld et al. have shown⁷ that this approach is, in some ways, equivalent to the power prior approach of Ibrahim and Chen⁸, whereby historical studies are assigned a fractional weight whose magnitudes correspond to the consistency of their data with that of the study they are thought to inform. Under the Empirical Bayes IPD meta-analysis model, covariates that may explain differences between studies will be retrieved, converted to similar scales and be included in the model for statistical adjustments. The selection of covariates will be pseudo informal, partially guided by expert advice and partially guided for *forward selection*.

4.4. Subject Disposition

A tabulation of subject disposition will be tabulated, including the number screened, the number dosed with each experimental drug(s) and control, the number in each subject population for analysis, the number that withdrew prior to completing the study, and reasons for withdrawal.

A by-subject listing of study completion information, including the reason for premature study withdrawal, if applicable, will be presented.

4.5. Demographic and Baseline Characteristics

Baseline, demographic and medical history information will be summarized for the <XX, XX and XX populations> using descriptive statistics. No formal statistical comparisons will be performed.

Demographic and Baseline data will be provided in data listings.

Statistical Analysis Plan

Sponsor:	McMaster University		
Protocol:	TOGETHER trial		
Document Version No.:	1.1	Document Date:	05-May-2021

4.6. Efficacy Evaluation

Efficacy analysis will be conducted using the ITT and PP Populations as outlined below. The two primary endpoints will be analyzed as a composite. Secondary endpoints will be assessed within 28 days of randomization, unless stated differently.

Table 3: Objectives and Endpoints

Objectives	Endpoints
Primary	

 Reduction in the need for emergency room visits due to the clinical worsening of COVID-19 and keeping the participant under observation for > 6 hours within 28 days of randomization in acutely affected patients and with evidence of high-risk for complications 	
 Proportion of those in need of emergency care under observation for more than 6 hours for COVID-19

 Reduction in the need for hospitalization due to the progression of COVID-19 (worsening of viral pneumonia) or complications within 28 days of randomization in acutely affected patients and with evidence of high-risk for complications 	
 Proportion of those in need of hospitalization due to progression of COVID-19 and/or complications
Secondary	

 To test the efficacy of experimental interventions to reduce SARS-CoV-2 viral shedding at day 3 and day 7 	
 Proportion of persons with clearance of SARS-CoV-2 from nasal swabs or saliva, defined as 1 negative swab Proportion of days with SARS-CoV-2 detected from mid-nasal swabs by PCR Change in viral load on day 3 and day 7 compared to baseline

 To test whether any of the experimental interventions decrease time to resolution for symptomatic SARS-CoV-2 infection / COVID-19 disease 	
 Time to clinical improvement (up to 28 days of randomization), defined as the first day on which the participant reports a score of 0 on the WHO Clinical Worsening Scale

Statistical Analysis Plan

Sponsor:	McMaster University		
Protocol:	TOGETHER trial		
Document Version No.:	1.1	Document Date:	05-May-2021

	
 • Time to clinical failure • Number of days with respiratory symptoms after randomization • Proportion of patients on each scale of the WHO clinical worsening scale over the treatment period and over the follow-up period

 • To test whether any of the experimental interventions is associated with decreased mortality within 28 days of randomization 	
 • Proportion of participants who died due to any cause • Proportion of participants who died due to pulmonary complications • Proportion of participants who died due to cardiovascular complications

 • To test whether any of the experimental interventions is associated with decreased hospitalization for any causes 	
 • Proportion of participants hospitalized due to any cause

 • To test whether any of the experimental interventions is associated with the time of hospitalization due to COVID-19 	
 • Time to hospitalization due to COVID-19 progression

 • To test the quality-of-life (QoL) of experimental interventions for treatment of high-risk outpatients with SARS-CoV-2 infection 	
 • Change in quality of life measured by PROMIS Global-10 from baseline to Day 14 and Day 28

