2.4. Study Procedures

As outlined in the study protocol, the schedule of assessment is provided in Table 1.

Statistical Analysis Plan

Sponsor:	McMaster University		
Protocol:	TOGETHER trial		
Document Version No.:	1.1	Document Date:	05-May-2021

Table 1. Schedule of Study Activities

	Screening and Treatment Period ⁹								Post-treatment Period ⁹			
	Screening Visit (D-0)	Baseline and Randomization (1) D-0	Day 1	Day 2 ⁽⁴⁾	Day 3 ⁽⁴⁾ ± 1 day	Day 4 ⁽⁴⁾	Day 5 ⁽⁴⁾	Day 7 ⁽⁴⁾ ± 1 day	Day 10 ± 2 days	Day 14 ⁽⁴⁾ ± 2 days	Day 28 ⁽⁴⁾ ± 3 days	Day 60 ^(4,8) or Early Termination ± 5 days
Informed Consent	X											
SARS-CoV2 Rapid Test	X ⁽¹⁾											
Eligibility Criteria Review	X ⁽²⁾											
Pregnancy Test	X ⁽³⁾											
Demographics	X ⁽⁵⁾											
Co-morbidities and Risk Factors	X											
Medical History	X											
WHO Clinical Worsening Scale	X		X	X	X	X	X	X	X	X	X	X
Temperature, Arterial O ₂ Saturation		X										
Exposure to Index Case Information		X										
Substance Abuse		X										
PROMIS Global Health Scale		X ⁽⁶⁾								X ⁽⁶⁾	X ⁽⁶⁾	X ⁽⁶⁾
ECG		X										
Height and Weight		X										
Nasopharyngeal Swab		X			X			X				
Randomization		X										
Concomitant Medications		X	X	X	X	X	X	X	X	X	X	X
Investigational Treatment Administration			X ⁽⁷⁾	X ⁽⁷⁾	X ⁽⁷⁾	X ⁽⁷⁾	X ⁽⁷⁾	X ⁽⁷⁾	X ⁽⁷⁾			

Statistical Analysis Plan

Sponsor:	McMaster University		
Protocol:	TOGETHER trial		
Document Version No.:	1.1	Document Date:	05-May-2021

Hospitalization / Emergency Room Visits			X	X	X	X	X	X	X	X	X	X
Respiratory Symptoms			X	X	X	X	X	X	X	X	X	X
Adverse Events			X	X	X	X	X	X	X	X	X	X
Adverse Drug Reactions			X	X	X	X	X	X	X	X	X	X
Vaccination Status										X	X	X

Legend

1. Screening and baseline visit: must be carried out at the same time when attending the outpatient setting. Rapid antigen test for COVID-19 at the screening visit. Day 1 visit should also be conducted on the same day as the screening and baseline visit. After completing the screening visit procedures at the baseline visit and present all inclusion / exclusion criteria, participants should be immediately randomized. The first dose of treatment under investigation must be administered on the same day of randomization (immediately after randomizing). The study medication will be administered as prescribed. Patients must be observed for 30 minutes after the medication administration.

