2.5. Efficacy and Safety Variables

2.5.1. Efficacy Variables

Primary endpoint:

- Emergency room visit due to the clinical worsening of COVID-19 (defined as participants remaining under observation for > 6 hours) within 28 days of randomization
- Hospitalization due to the progression of COVID-19 (defined as worsening of viral pneumonia) and/or complications within 28 days of randomization

Secondary endpoints:

- Viral clearance and viral load on D3 and D7 after randomization;
- Time (in days) to clinical improvement (up to 28 days of randomization), defined as the first day on which the participants report a score of 0 on the World Health Organization (WHO) Clinical Worsening Scale;
- Time (in days) to clinical failure;
- Number of days with respiratory symptoms since randomization;
- Hospitalization for any causes;
- Time to hospitalization due to COVID-19 progression;
- Mortality due to pulmonary complications;
- Mortality due to cardiovascular complications;
- Mortality from any causes;
- Adverse events that occurred (up to 28 days);
- Adverse drug reactions;
- WHO clinical worsening scale over the follow-up period;
- WHO clinical worsening scale during the treatment phase;
- PROMIS global health scale scores (days 14 and 28).

Statistical Analysis Plan

Sponsor:	McMaster University		
Protocol:	TOGETHER trial		
Document Version No.:	1.1	Document Date:	05-May-2021

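### Two of the three virology endpoints in SAP Table 3 do not fit the swabs scheduled in Table 1: one cannot be obtained from them, and clearance is defined without a positive baseline.

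*SAP*

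**What the plan says.** Three places in the SAP describe the virology.

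- **Section 2.4, Table 1 (schedule).** The row "Nasopharyngeal Swab" is marked at baseline, Day 3 and Day 7, and nowhere else. No saliva, nasal or mid-nasal sample has a row. The only other viral test is the one used for entry: "Rapid antigen test for COVID-19 at the screening visit".
- **Section 2.5.1.** One virology item is listed: "Viral clearance and viral load on D3 and D7 after randomization".
- **Section 4.6, Table 3.** The objective is to "reduce SARS-CoV-2 viral shedding at day 3 and day 7". Three endpoints stand against it:
  1. "Proportion of persons with clearance of SARS-CoV-2 from nasal swabs or saliva, defined as 1 negative swab"
  2. "Proportion of days with SARS-CoV-2 detected from mid-nasal swabs by PCR"
  3. "Change in viral load on day 3 and day 7 compared to baseline"

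Section 4.6 applies the efficacy analysis to the ITT and PP populations, and section 3.1 defines ITT as every randomized patient. No narrower set is given for virology.

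**The concern.** The second endpoint asks how many days a patient was PCR-positive, but patients are swabbed on two days after baseline. The SAP gives neither a denominator of days nor a rule for unsampled days, so the analyst would have to invent both. The specimen is also not the one scheduled, and section 2.5.1 does not list the endpoint.

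The first endpoint has a specimen mismatch of its own: neither of its specimens is scheduled, and a saliva sample cannot meet a definition that requires a swab. Its second weakness is that nothing requires virus to have been detected by PCR at baseline. Entry rests on an antigen test, so a positive baseline PCR is not guaranteed. Under the literal definition, a patient who is negative throughout counts as cleared. At stake are the interpretability of two secondary endpoints and some loss of contrast in clearance.

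**Working it through.** The SAP states no figure to reproduce. The check sets the endpoints against the schedule.

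**1. What swabs on Days 0, 3 and 7 can show**

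Inputs: swab days from Table 1, and the Day 3 and Day 7 horizon from the Table 3 objective and section 2.5.1. Assumption, not in the SAP: shedding is continuous from a positive baseline to one last positive day.

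Days covered after baseline: 2 of 7 = 28.6%. Including baseline: 3 of 8 = 37.5%.

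| Day 3 | Day 7 | Last positive day | Score on sampled days | True share of Days 1–7 |
|---|---|---|---|---|
| neg | neg | 0 to 2 | 0/2 = 0 | 0/7 to 2/7 = 0% to 28.6% |
| pos | neg | 3 to 6 | 1/2 = 0.5 | 3/7 to 6/7 = 42.9% to 85.7% |
| pos | pos | 7 or later | 2/2 = 1 | 7/7 = 100% |

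The middle pattern fits true values that differ by a factor of two (6/7 against 3/7). If shedding may be intermittent, the ranges widen, and a patient negative on Day 3 but positive on Day 7 also scores 0.5. What can be computed is the share of swabs that were positive.

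**2. Specimens**

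| Endpoint in Table 3 | Specimen named | Scheduled in Table 1? |
|---|---|---|
| Clearance | nasal swab or saliva | no |
| Days detected | mid-nasal swab | no |
| Viral-load change | none named | days match; no conflict |

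The mismatch therefore affects two endpoints of three.

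**3. Effect of baseline PCR-negatives on clearance**

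Let f be the share PCR-negative at baseline who stay negative, taken as equal in both arms by randomization, and let p be true clearance among baseline-positives.

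- Observed clearance = f + (1 − f)p
- Rise over p = f(1 − p), which is larger in the arm with lower clearance
- Observed difference = (1 − f)(p₁ − p₀)

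Illustration with assumed clearance of 40% and 50% (true difference 10 points):

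| Assumed f | Arm at 40% | Arm at 50% | Difference |
|---|---|---|---|
| 5% | 0.05 + 0.95 × 0.40 = 43.0% | 0.05 + 0.95 × 0.50 = 52.5% | 9.5 points |
| 10% | 0.10 + 0.90 × 0.40 = 46.0% | 0.10 + 0.90 × 0.50 = 55.0% | 9.0 points |

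The loss is 5% and 10% of the true difference. It applies to the difference in proportions. The ratio of patients still positive is unchanged: at f = 10%, 45/54 = 0.83, the same as 50/60.

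**The case against.** The strongest reply is that Table 3 should be read row by row. The objective beside these endpoints is limited to Day 3 and Day 7, so the days-based measure can be taken as detection over the sampled days: coarse and badly named, but computable. Part of this stands. A reader might apply the 28-day default for secondary endpoints and say that swabs cover only 2 of 28 days. That default yields where something else is stated, and this row states its own days. The seven-day horizon is the fair one, and even on it the quantity named is not identified.

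A reader might also infer that mentioning both nasal swabs and saliva lets a change of specimen pass for clearance. The document gives no route for that: no saliva is scheduled, and clearance requires a swab. The wording is wrong, but no bias follows from it. Nor are all three endpoints at fault, since the viral-load bullet matches the schedule and names no conflicting specimen.

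On baseline negatives, it can be said that clearance already implies earlier detection, and that randomization balances such patients in expectation. The first is a reasonable reading, but the definition given does not say it and the default population is everyone randomized. The second is right, and it means the consequence is attenuation, not a spurious drug effect. Restricting the set is partly a choice of estimand, and it narrows the ITT set.

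**Conclusion.** The point holds, at low consequence. One listed secondary endpoint cannot be delivered by the design: two post-baseline swabs yield 0, 0.5 or 1 as a share of swabs, and the same result can fit anything from 42.9% to 85.7% of days under continuous shedding. Two endpoints name specimens that are not scheduled. Clearance, read literally in the ITT set, includes patients with no PCR-detectable virus at baseline. The difference between arms then shrinks by the factor (1 − f), or 5–10% if f is 5–10%. That range is an assumption; the document gives no baseline PCR-negative share.

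It would be a stretch to conclude that the virology results as a whole are invalid or could favour a drug falsely. Viral-load change fits the schedule; the baseline-positive condition is worth applying there only because a fall cannot be measured from an undetectable start. The primary composite, the sample size and the stopping rules do not depend on any of this.

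**What to change.** In Table 3:

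- Delete the days-based bullet. Among baseline-positive patients with a swab result, detection at Day 3 and at Day 7 is simply the complement of clearance on those days, so a renamed version would report the same result twice.
- Define clearance as a PCR-negative scheduled nasopharyngeal swab, at Day 3 and at Day 7 separately, among randomized patients PCR-positive on the baseline swab. State the assay in this definition, because the deleted bullet is the only one of the three that mentions PCR.
- Use the same baseline-positive patients for change in viral load, and name the nasopharyngeal specimen there too.
- Describe this set as a subset of ITT defined by the baseline swab, and report its size by arm.

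This brings Table 3 into line with section 2.5.1 and the schedule. It changes wording only and needs no further samples. The cost is a slightly smaller denominator. Because the condition rests on a swab scheduled at the baseline visit, the comparison between randomized arms is kept.
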